The purpose of the proposed study is to validate that the definition of moderate to severe influenza in children predicts greater risk of healthcare endpoints such as hospitalization, increased length of stay, use of antimicrobials (including antivirals), absenteeism, increased duration of illness, and increased healthcare costs.

Understanding and validating the relationship between moderate to severe influenza and these clinically relevant endpoints is critical to establishing relevant surrogate markers of clinical and public health outcomes. If shown to be clinically relevant, this definition of moderate to severe influenza can be an important endpoint for assessing influenza vaccine effectiveness.

III. Preliminary Studies/Progress Report:

CHCO provides an ideal site for the study of influenza in children. CHCO is a large tertiary institution with a large catchment area of Denver Metro, Aurora and surrounding states. It serves 67% of children in the state of Colorado. From December 1, 2010 to April 30, 2014, there were 409 patients admitted to CHCO with PCR-confirmed influenza; 62% of these were defined as high-risk (16), and 38% were vaccinated against influenza during the same season. Accurate immunization data was available for 83% of patients via the Colorado Immunization Information System (CIIS). Clinical presentation and

hospital-based outcomes such as length of hospitalization among children admitted with influenza are shown in Table 1.

Table 1. Children Admitted To CHCO with Influenza, 2010-2014

Children admitted to CHCO with influenza N = 395	< 3 years N = 156	>3 years N = 239
Otitis media	10 (6)	6 (3)
Pneumonia	7 (5)	22 (9)
Hypoxia	19 (12)	141 (59)
Fever	133 (85)	207 (87)
Median duration of fever, days (range)	2 (1-17)	4 (1-64)
Tachypnea	64 (41)	91 (38)
Antibiotics	88 (56)	157 (66)
Median duration of antibiotics, days (range)	7 (0-23)	8 (0-77)
Pediatric Intensive Care Unit (PICU)	55 (35)	81 (34)
PICU length of stay, days	2 (1-100)	3(1-83)
Death	1 (1)	2 (1)
Median duration of hospitalization, days (range)	3 (1-100)	3 (1-128)
Vaccinated during current season against influenza	39 (25)	87 (36)

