Preliminary data from the 2013-2014 and 2014-2015 influenza seasons demonstrated that among 11,997 patients who presented to CHCO ED, UC or outpatient clinics for an acute respiratory illness, 1398 (12%) underwent viral testing (either respiratory pathogen panel multiplex PCR or influenza PCR). 1375 patients were admitted for a respiratory illness, and of these, 994 (72%) underwent viral testing. Additional data regarding ED visits during these time periods are shown in Table 2.

Table 2. Children Presenting to CHCO ED or UC with Acute Respiratory Illness, 2013-2014 and 2014-2015

CHCO data:	2013-2014	2014-2015	Total
ED/UC/Clinic visits due to an acute respiratory illness	5900	6097	11997
ED visits due to an acute respiratory illness, limited to patients < 8 yrs	4510	4595	9105
ED visits limited to CHCO, Uptown Urgent Care, South Urgent Care with an acute respiratory illness, limited to patients < 8 yrs	2703	2809	5512
ED visits with above restrictions further limited to Jan to March	1290	1745	3035
Limit visits to < 8 yrs Jan to March, no repeat visits	1244	1688	2932
Admission for acute respiratory illness,	454	486	940

Jan -Mar

IV. Research Methods

The study comprises a prospective analysis of children presenting to CHCO ED, and North Campus UC with an influenza-like illness (ILI) during the 2016-2017 influenza season. Once enrolled in the study, we will collect respiratory samples (nasopharyngeal (NP) specimens), socio demographic, and clinical data including variables of interest outlined above, and follow the clinical outcome of these children for 14 days after their initial presentation. A complete list of the variables being collected can be found in Appendix A.

A. Outcome Measure(s):

Primary outcome measure /Endpoints:

- 1) Hospitalization in patients presenting to the CHCO Main ED or North Campus UC with influenza

Secondary outcome measures/Endpoints:

- 1) ICU admission in patients presenting to the CHCO Main ED or North Campus UC with influenza
- 2) Antiviral use in patients presenting to the CHCO Main ED or North Campus UC with influenza
- 3) Antibiotic use in patients presenting to the CHCO Main ED or North Campus UC with influenza
- 4) Number of visits to the ED or healthcare provider in patients presenting to the CHCO Main ED or North Campus UC with influenza
- 5) Number of days of absenteeism from school or daycare in patients presenting to the CHCO Main ED or North Campus UC with influenza

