- f. Extrapulmonary complications in patients presenting to the CHCO Main ED or North Campus UC with ILI

Definitions:

Influenza like illness (ILI): child with temperature of $\geq 37.8^{\circ}\text{C}$ and at least one of the following: cough, sore throat, runny nose or nasal congestion

Influenza: child with respiratory test that is positive for influenza by PCR

Moderate to severe influenza: child with influenza and one or more of the following criteria:

1. fever $> 39^{\circ}\text{C}$,
2. presence of otitis media defined by AAP guideline criteria,
3. lower respiratory tract infection (shortness of breath, pulmonary congestion, pneumonia, bronchiolitis, bronchitis, wheezing, croup), or
4. serious extrapulmonary manifestations (e.g., myocarditis, encephalitis, seizure)(15).

Mild influenza: child with ILI symptoms, but do not have any of the criteria for moderate to severe influenza

SIRS: Defined as the presence of two or more of the following, one of which must be abnormal temperature or leukocyte count:

1. core temperature <36 or >38.5°C
2. tachycardia (or bradycardia in infants),
3. tachypnea

Modified SIRS criteria (18): same definition as SIRS criteria excluding neutrophil criteria, i.e. the presence of two or more of the following, one of which must be abnormal temperature :

1. core temperature <36 or >38.5°C
2. tachycardia (or bradycardia in infants),
3. tachypnea

Tachycardia and tachypnea definitions by age:

Age group	Tachycardia	Bradycardia	Respiratory rate
1 month-1 year	>180	<90	>34
2-5 years	>140	NA	>22
6-12 years	>130	NA	>18

B. Description of Population to be Enrolled:

Population:

Children 6 months to 8 years of age seeking evaluation and management of ILI at the Main CHCO ED or North Campus UC will be eligible for participation in the study. The study will commence during the influenza season as determined by the department of microbiology and epidemiology at CHCO (the influenza season commences when there are 3 positive influenza PCR tests within a week). The study will continue for 5 months following the start of the influenza season.

Inclusion criteria:

- 1) Age 6 months \leq 8 years
- 2) Presentation to the CHCO Main ED or North Campus UC with signs and symptoms of ILI (temperature of $\geq 37.8^{\circ}\text{C}$ and at least one of the following: cough, sore throat, runny nose or nasal congestion)
- 3) Patients seen during the 2016-2017 influenza season

Exclusion criteria:

- 1) Respiratory symptom duration $>$ 14 days

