For all study objectives, we will present data descriptively using frequencies for categorical variables and measures of central tendency for continuous variables. We will explore bivariable associations between moderate to severe versus mild influenza for covariates including demographic factors and clinical factors outlined above. Proportions will be compared using Chi-square test. Mean values will be compared using student's t test for normally-distributed data, otherwise Wilcoxon-Rank-Sum test will be used.

Aim #1/Primary Endpoint Analysis: We will use logistic regression to estimate odds ratios (and 95%CI) for hospitalization, adjusted for significant covariates at the level of $P < 0.2$ on bivariable analysis; and other covariates selected *a priori* that could affect outcomes such as hospitalization (age group, high risk medical condition, vaccination status, influenza type). We will verify to ensure statistical assumptions are met for each model. The intraclass correlation coefficient will be estimated and a multi-level model will be used if we need to account for multiple visits per child. If we use a multi-level model, the optimal covariance structure will be determined through the examination of information criteria statistics and graphical techniques.

Aim #2/Secondary Endpoint #1-6 Analysis: We will use logistic regression to estimate each of our dichotomous secondary outcomes of interest, ICU admission, antibiotic,

antiviral use, adjusted for significant covariates at the level of $P < 0.2$ on bivariable analysis; and other covariates selected *a priori* that could affect outcomes such as hospitalization (age group, high risk medical condition, vaccination status, influenza type). We will verify to ensure statistical assumptions are met for each model. The intraclass correlation coefficient will be estimated and a multi-level model will be used if we need to account for multiple visits per child. If we use a multi-level model, the optimal covariance structure will be determined through the examination of information criteria and graphical techniques. We will also explore our secondary outcomes of interest expressed as continuous variables (number of recurrent visits to the ED, duration of absenteeism in days). We will use a log linear model to compare these variables between the mild versus moderate to severe influenza groups and will exponentiate the coefficients to yield geometric mean ratios.

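### Age is named in the primary and secondary logistic models only as an undefined age group; a pre-stated spline in months would be a cheap safeguard against residual confounding by age

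*Combined protocol and SAP*

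**What the plan says.** Section IV.F (Data Analysis Plan) gives the same covariate rule under Aim #1/Primary Endpoint Analysis and under Aim #2/Secondary Endpoint #1-6 Analysis. Each logistic model is "adjusted for significant covariates at the level of $P < 0.2$ on bivariable analysis", and also for a list fixed in advance: "age group, high risk medical condition, vaccination status, influenza type". The candidates for the screen are "covariates including demographic factors and clinical factors outlined above". The plan adds: "We will verify to ensure statistical assumptions are met for each model".

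The age groups are not defined anywhere in the readable text. Two bandings appear for other purposes:

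- Table 1 in section III ("Children admitted to CHCO with influenza N = 395") splits historical inpatients at 3 years.
- The table in section IV.A headed "Tachycardia and tachypnea definitions by age" uses 1 month-1 year, 2-5 years and 6-12 years for vital signs.

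Neither is tied to the models. Section IV.B sets the population: "Children 6 months to 8 years of age seeking evaluation and management of ILI".

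**The concern.** Aim 1 asks whether the moderate-to-severe definition predicts hospitalization. The definition is built from fever, otitis media, lower respiratory illness such as bronchiolitis and croup, and serious extrapulmonary events. Several of these plausibly vary with age, and so may the decision to admit. The plan itself counts age among the factors that could affect hospitalization.

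A grouped age term removes differences between bands but not within them. Whatever remains goes into the odds ratio for moderate-to-severe disease and would be credited to the definition. That matters because the stated purpose is to support the definition as an endpoint for vaccine studies. With no cut-points stated, the coding can also be chosen after the data are seen.

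**Working it through.** **The plan's own figures.** The plan gives no figure for the age term. Its testing targets reproduce: 408/0.25 = 1632 and 151/0.25 = 604. Neither depends on how age is coded.

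**Model for the check (all assumed).** Let z be age, or a function of age, in standard deviations, and let E = 1 for moderate-to-severe disease.

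- logit P(E = 1) = a + s1·z
- logit P(hospitalized) = b + s2·z + ln(OR)·E

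Age is uniform from 0.5 to 9 years and 70% have E = 1 (the plan's split). The fitted OR is compared across codings of age.

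**True OR 1, 30% hospitalized, s1 = s2 = 0.6, 2,000,000 records per scenario.**

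| Age effect | No age term | Two groups (<3, ≥3) | Three groups (<2, 2-4, ≥5) | Quarter-year |
|---|---|---|---|---|
| Linear | 1.40 | 1.16 | 1.07 | 1.01 |
| Log age | 1.37 | 1.10 | 1.05 | 1.005 |

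Relative to fine adjustment, the linear case leaves 1.16/1.01 = 1.15 (two groups) and 1.07/1.01 = 1.06 (three groups). With linear slopes of 0.2 the fitted ORs are 1.017 and 1.007.

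**True OR 2, 20% hospitalized, same age effect on severity and on hospitalization.** The SD of age is 8.5/√12 = 2.45 years, so an OR of 0.9 per year is 0.105 × 2.45 = 0.26 log-odds per SD, and 0.8 per year is 0.223 × 2.45 = 0.55.

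| OR per year | No age term | Two groups | Three groups (<2, 2-5, 6+) | Continuous |
|---|---|---|---|---|
| 0.9 | 2.11 | 2.04 | 2.01 | 1.99 |
| 0.8 | 2.64 | 2.26 | 2.14 | 2.05 |

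Relative to continuous age, two groups leave 2.04/1.99 = 1.03 and 2.26/2.05 = 1.10. Three groups leave 2.01/1.99 = 1.01 and 2.14/2.05 = 1.04.

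**Direction.** With opposite signs (s1 = -0.3, s2 = +0.6, linear, true OR 1) the two-group OR is 0.93. The error can therefore go either way.

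**Across shapes.** For linear, log and infant-concentrated effects of either sign, with slopes of 0.2-0.6, two groups missed by about 1-15%, three groups by about 0-7%, and the spline by no more than about 2%. These are ranges for the curves tried, not bounds. In a further check, an effect confined more sharply to infancy, with opposite signs, left more under every coding, including a 3-knot spline. Both splines still came closer than either grouping.

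**Linear age is not a safe substitute.** With an infant-concentrated effect and true OR 2, linear age gave 2.09, three groups 2.05 and the true curve 2.01.

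**Scale.** Assume 20% of mild cases are hospitalized (the readable text gives no rate). With OR 2 the other rate is 0.4/1.2 = 0.333.

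- Variance term: 1/(0.3 × 0.2 × 0.8) + 1/(0.7 × 0.333 × 0.667) = 20.83 + 6.43 = 27.26
- SE of ln(OR) at 408: √(27.26/408) = 0.258
- 95% limits: a factor of exp(1.96 × 0.258) = 1.66 either side
- A 7% error is ln(1.07)/0.258 = 0.26 SE; a 15% error is ln(1.15)/0.258 = 0.54 SE

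**Cost.** In 1,500 replicates at 408 patients, a 4-knot spline raised the SE of ln(OR) by about 2-6% over two groups and 1-2% over three. At true OR 1 and slope 0.6, the false-positive rate was 6-9% with two groups; with the spline it was 4-6%.

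**The case against.** The strongest reply is that age categories fixed in advance are common and acceptable, and that age group does not mean coarse. In the true-OR-2 setting, yearly groups came close to continuous age. The larger errors come from the two-band split, which belongs to a description of past inpatients and is nowhere named as the model covariate. The slopes and their signs are assumed. If age does not affect severity class there is no confounding to leave behind. All of this stands, and it is why the point is a risk of modest size.

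A reader might infer more from the text than it supports:

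- **That age can enter only in groups.** The P < 0.2 screen covers demographic factors and does not exclude continuous age, and model assumptions are to be checked. But nothing commits the analyst to continuous age.
- **That Table 1 shows a steep age gradient.** It covers admitted children only, and the directions are mixed: below versus above 3 years, otitis media is 6% v 3%, pneumonia 5% v 9%, fever 85% v 87%, tachypnea 41% v 38% and intensive care 35% v 34%. Hypoxia differs sharply (12% v 59%). None of this measures the effect of age on severity class or on admission among children presenting for care.
- **That exact age is documented.** The plan says "A complete list of the variables being collected can be found in Appendix A", but that appendix is only partly present in the text supplied. Exact age is a fair inference from the eligibility limits.

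The reply does not remove the case for the change. The cut-points are unstated, and the alternative costs almost nothing.

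**Conclusion.** The point holds as a cheap improvement. Age is named in advance only as an undefined grouping in both sets of logistic models, and grouping can leave residual confounding in either direction. The sizes above (about 0-7% with three groups, 1-15% with a split at 3 years) rest on assumed slopes of 0.2-0.6 per SD, assumed shapes, and age uniform from 0.5 to 9 years.

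It would go too far to say that the primary odds ratio is biased by a known amount, or that bias of 25% or so is in prospect. That figure needs both the two-band split and slopes near 0.8 per SD, and the documents support neither. Even 15% is about half a standard error at 408 patients, and the sample size is unaffected.

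**What to change.** In section IV.F, in both the Aim #1 and the Aim #2 paragraphs, replace age group with age in months, modelled as a restricted cubic spline with 3 or 4 knots at stated positions. State that this is the only age term, so that the P < 0.2 screen does not add a second. Keep age groups for descriptive tables or as a sensitivity analysis, with cut-points stated. For the sparser intensive care model use a 3-knot spline, not linear age.

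Age in months should be available from the date of birth needed to check eligibility; the team should confirm this against the full Appendix A.

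A spline with 3 or 4 knots uses 2 or 3 degrees of freedom, against 1 for two groups and 2 for three. The primary model can carry that. Under the assumed 20% mild rate and OR 2, expected hospitalizations are 408 × (0.3 × 0.2 + 0.7 × 0.333) = about 120. The confidence interval widens slightly (about 1-6% in standard error). No new visit, sample or data item is needed.

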- 6) Number of days of absenteeism from work in caregivers of children presenting to the CHCO Main ED or North Campus UC with influenza
- 7) Healthcare costs associated with ED visits or hospitalization in patients presenting to the CHCO Main ED or North Campus UC with influenza

Exploratory Outcome measures/Endpoints:

1) Vaccination status in subjects testing positive for influenza:

- a. Injectable influenza vaccine (IIV) receipt in patients presenting to the CHCO Main ED or North Campus UC with moderate to severe influenza
- b. IIV receipt in patients presenting to the CHCO Main ED or North Campus UC who are hospitalized
- c. IIV receipt in patients presenting to the CHCO Main ED or North Campus UC who are admitted to the ICU
- d. Number of days of fever in patients who received IIV presenting to the CHCO Main ED or North Campus UC
- e. Number of days of caregiver and child absenteeism in patients who received IIV presenting to the CHCO Main ED or North Campus UC

- f. IIV receipt in patients presenting to the CHCO Main ED or North Campus UC who received antibiotics
- g. IIV receipt in patients presenting to the CHCO Main ED or North Campus UC who received antivirals

2) Influenza-like-illness among subjects testing negative for influenza:

- a. Hospitalization in patients with ILI who test negative for influenza
- b. ICU admission in patients with ILI who test negative for influenza
- c. Duration of fever in patients with ILI who test negative for influenza
- d. Number of days of absenteeism from work in caregivers of patients with ILI who test negative for influenza
- e. Number of days of absenteeism from school in patients with ILI who test negative for influenza
- f. Antibiotic use in patients with ILI who test negative for influenza
- g. Antiviral use in patients with ILI who test negative for influenza

3) Fever, vital sign data and extrapulmonary complications:

- a. Number of days of fever in patients presenting to the CHCO Main ED or North Campus UC with influenza
- b. Peak temperature at any time during illness in patients presenting to the CHCO Main ED or North Campus UC with influenza
- c. Modified SIRS criteria met in patients presenting to the CHCO Main ED or North Campus UC with influenza
- d. Initial and peak adjusted heart rate in patients presenting to the CHCO Main ED or North Campus UC with influenza
- e. Oxygen saturation in patients presenting to the CHCO Main ED or North Campus UC with influenza

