- 2) Prior enrollment in study
- 3) Nurse only visit

C. Study Design and Research Methods

[figure not shown]
This will be a prospective observational cohort study conducted at the CHCO Main ED and North Campus UC.

Surveillance Methods:

The study group will review the CHCO Main ED or North Campus UC visits for patients meeting study criteria presenting with ILI. Screening will be conducted by designated professional research assistants (PRAs) at each site. The study team has a treatment relationship with potential subjects, since one of the co-investigators is an ED physician, thus enabling screening of potential patients. The parents/legal guardians of eligible patients will be approached for consent to obtain respiratory specimens for PCR testing, interviewed to obtain medical information pertaining to the current and future ILI visits, asked permission to obtain additional information (vaccination status, influenza vaccination type [LAIV] or IIV) and medical comorbidities) from the primary care provider, and to bank residual blood and respiratory samples. A memory aid card will be provided to the family member upon discharge from the ED/UC setting as an aide memoire, and the medical chart will be reviewed for additional clinical and demographic information. On day 14(+/-3) following the initial visit, caregivers of all participants who test positive for influenza will be contacted by phone to provide additional follow-up information regarding child and parental absenteeism, additional healthcare visits, duration of illness. Additionally, a random sample of participants whose influenza test is negative in a 1 to 4 ratio will be contacted for follow-up. A second chart review will occur at this time for details regarding additional visits or admissions. Data will be managed with REDCap (Research Electronic Data Capture) tools hosted at the University of Colorado (19) and exported to SAS 9.3 (Cary, NC) for statistical analyses.

A flow diagram summarizing the study methods is shown in Figure 1.

Figure 1. Flow diagram summarizing methods for proposed surveillance study

Specimen Testing:

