Patients will be assigned a sequential study number for the database that will have no relationship to any patient identifying information. The legend will be maintained until data editing is complete, and then the link will be destroyed. During the study period, the legend will be stored in a secure manner in a locked room with limited access, and computerized data will be similarly maintained in a secure fashion by the study team at CHCO. Data will only be publicly presented in aggregate form. This minimizes the risks related to invasion of privacy and breach of confidentiality.

E. Potential Scientific Problems:

A potential limitation of the study is potential selection bias due to the inability to test all patients who present with ILI to the ED. This is due to a high volume of patients presenting to the ED, as shown in Table 1. We will select patients based on age, restrict the season to once the influenza season has commenced, and will attempt to include all patients during this time period, which aims to avoid the skewing of data to more patients with co-morbidities or higher severity of illness who will undergo testing during routine clinical care.

There is also a possibility for recall bias regarding vaccination status and other medical history obtained from the parents/legal guardians. We will verify this information with the electronic medical record, which is linked to the CIIS. The CIIS is a lifelong immunization record tracking system managed by the Colorado Department of Public Health and Environment (CDPHE). Approximately 85% of Colorado primary care practices utilize the registry. In addition, if vaccination status cannot be determined from the electronic medical record, a member of the study team will contact the primary care Physician (PCP) for vaccination information. The combination of verification from the PCP as well as the CIIS registry will increase the accuracy of influenza vaccination status.

The study may have limited external validity and cannot provide population-based estimates of moderate to severe influenza, given its design.

F. Data Analysis Plan:

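### The Aim 1 and Aim 2 models provide for repeat visits by a child, although each child enrols once, and not for siblings; intervals can be slightly too narrow and one caregiver's lost work days can count twice

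*Combined protocol and SAP*

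**What the plan says.** All references are to the combined protocol and SAP.

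- **Section IV.F, Aim 1, repeated under Aim 2.** An intraclass correlation will be estimated, and "a multi-level model will be used if we need to account for multiple visits per child". This is the only clustering provision for these regressions.
- **Section IV.B, exclusion criteria.** One of the three exclusions is "Prior enrollment in study". None of the three concerns a sibling already in the study.
- **Section IV.B, population.** Eligible are "Children 6 months to 8 years of age seeking evaluation and management of ILI" at the two sites. Section IV.E adds that the study "will attempt to include all patients during this time period".
- **Section IV.A, secondary endpoint 6.** "Number of days of absenteeism from work in caregivers of children presenting to the CHCO Main ED or North Campus UC with influenza". Section IV.C gives the source: at about day 14, "caregivers of all participants who test positive for influenza will be contacted by phone".
- **Section IV.F, Aim 2, absenteeism and recurrent visits.** "We will use a log linear model to compare these variables between the mild versus moderate to severe influenza groups". No clustering term is named.
- **Section IV.D.** The key linking study numbers to patients is kept only until data editing ends, and is then destroyed.

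The available text mentions no sibling, household or family identifier.

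**The concern.** The authors recognised that observations might not be independent, but the unit they named is one the enrolment rules largely remove. A child enters once, and further visits are counted as secondary endpoint 4, so the Aim 1 and Aim 2 outcomes should have one row per child.

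The dependence that remains possible is within families. Influenza is contagious, the age range easily covers two or more children in a household, and the study tries to enrol everyone eligible. Siblings may share vaccination history, virus type and a parent's threshold for seeking care. If their outcomes are correlated and they fall in the same severity group, an unclustered model overstates the information in the data.

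Endpoint 6 is the most exposed because its subject is the caregiver. If two siblings test positive, the same parent may report the same lost days once for each child, and one person's outcome then enters as two records.

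**Working it through.** **1. The plan's own figures.** Section IV.F assumes 25% of those tested are positive: 408 / 0.25 = 1632 and 151 / 0.25 = 604, both as stated. The 408 itself cannot be verified, because neither the hospitalization rate in mild cases nor the covariate R-squared is given. Without covariate inflation, a mild-case rate of about 0.204-0.220 fits both 408 (odds ratio 2) and 151 (odds ratio 3) within 3%. Nothing below depends on that rate.

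**2. Formula.** The planned analyses compare mild with moderate-to-severe cases. For sibling pairs, let

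- f = share of analysed (influenza-positive) children with an analysed sibling,
- ρ = correlation of the siblings' outcomes, given the covariates,
- r = correlation of the siblings' severity groups.

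With n children and a proportion p in one group, the within-pair cross-products of the group indicator sum to n·f·r·p(1−p), against n·p(1−p) for the children's own squared terms. The variance of the contrast is therefore multiplied by

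DEFF = 1 + f·ρ·r,

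and the true standard error is √DEFF times the unclustered one. This is exact for a linear contrast and approximate for a logistic model. The simpler 1 + f·ρ applies to a group mean, or to the contrast only when r = 1.

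**3. Results.** None of f, ρ and r is in the documents; all are assumptions.

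| Outcome | f | ρ | r | DEFF | True SE / reported SE | Coverage of nominal 95% CI |
|---|---|---|---|---|---|---|
| Hospitalization | 0.10 | 0.3 | 0.6 | 1.018 | 1.009 | 94.8% |
| Hospitalization | 0.20 | 0.3 | 1.0 | 1.060 | 1.030 | 94.3% |
| Caregiver days | 0.05 | 0.9 | 0.3 | 1.014 | 1.007 | 94.8% |
| Caregiver days | 0.10 | 0.9 | 0.6 | 1.054 | 1.027 | 94.4% |
| Caregiver days | 0.20 | 0.9 | 1.0 | 1.180 | 1.086 | 92.9% |
| Caregiver days | 0.20 | 0.9 | 0 | 1.000 | 1.000 | 95.0% |
| Caregiver days | 0.20 | 0.9 | −0.3 | 0.946 | 0.973 | 95.6% |

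For example, 1 + 0.10 × 0.9 × 0.6 = 1.054, and √1.054 = 1.027.

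**4. Primary endpoint.** The effective sample is 408 / 1.018 = 401 in the first hospitalization row and 408 / 1.060 = 385 in the second. Nominal 80% power becomes 79.3% and 77.7%.

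**5. Check by simulation.** An unclustered analysis of 408 children with ρ = 0.9 gave type I error of about 5.5-5.6% at f = 0.10 with r = 0.3-0.6, about 7.2% at f = 0.20 with r = 1, and about 5% when sibling severity groups were unrelated. This agrees with the formula.

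**6. Double counting in endpoint 6.** If siblings fall in different severity groups, the same lost days enter both arms of the comparison and pull the geometric mean ratio towards 1. No standard error correction removes that.

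**The case against.** The strongest reply is that the harm depends on facts the documents do not contain. Both siblings must be enrolled and PCR-positive, their outcomes must be correlated, and their severity groups must agree. If the groups are unrelated the unclustered interval is correct, and if they are discordant it is slightly too wide. That stands. A reader might infer that the intervals are too narrow, or that type I error exceeds 5%, as established facts; the documents do not support that.

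Other replies also have force:

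- The logistic models adjust for vaccination status and influenza type, two of the factors siblings share, so the residual correlation may be lower than assumed.
- The exclusion bars re-enrolment, not repeat visits, and the multi-level clause is conditional. An unused contingency does no harm in itself, so it would go too far to say that the models cluster on the wrong unit.
- It is also too strong to say that the plan decides to treat siblings as independent. It is silent on them, and most of Appendix A, the variable list, is missing from the available text, so a family identifier may already be collected.
- Caregiver absenteeism is one of seven secondary endpoints, and its analysis is introduced as exploration.

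Two replies do not remove the point. The general promise to verify model assumptions cannot reveal family clustering unless families are identified. The linear mixed model elsewhere in section IV.F handles repeated temperatures within a child, not families.

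**Conclusion.** The structural point holds on the text alone. The only clustering provision for Aims 1 and 2 concerns repeat visits, each child enrols once, siblings are not excluded, and no family-level clustering is planned. The consequence is conditional: intervals can be too narrow, not that they are.

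With 10-20% of analysed children in pairs and r from 0.6 to 1.0, the standard error is understated by about 1-3% for hospitalization and about 3-9% for caregiver absenteeism. The upper ends need complete agreement of severity group within pairs. The primary result would hardly change. Endpoint 6 deserves attention mainly because one caregiver's days can be entered twice. Severity: minor.

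**What to change.** 1. In the Aim 1 and Aim 2 paragraphs of section IV.F, reconcile the repeat-visit clause with the exclusion of children already enrolled: either delete it or say which analysis could have more than one row per child.
2. Record a family identifier in REDCap, or confirm that Appendix A already has one, before the study link is destroyed. After that, families may not be recoverable.
3. Use family-clustered standard errors (GEE or robust) in the Aim 1 and Aim 2 models.
4. For endpoint 6, count each caregiver's lost days once, with a rule set in advance for siblings in different severity groups, or add a sensitivity analysis with one child per family. Clustered standard errors alone do not solve this.

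The cost is one data field, one model option and possibly slightly wider intervals. No extra patients or procedures are needed. If an identifier is already collected, only the analysis text changes.
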